## 6.5 POOLING OF CENTRES

This section is not applicable, because the study was performed in only one centre.

## **6.6 HANDLING OF MISSING DATA AND OUTLIERS**

Handling of missing data and outliers will be performed as described in the CTP, Section 7.5.

The only exceptions where imputation might be necessary for safety evaluation are AE dates. Missing or incomplete AE dates are imputed according to BI standards (see BI-KMED-BDS-HTG-0035 ([4](#))).

Missing data and outliers of PK/PD data are handled according to BI standards (see 001-MCS-36-472\_RD-01) ([5](#)).

## **6.7 BASELINE, TIME WINDOWS AND CALCULATED VISITS**

The baseline value is defined as the last measurement before trial medication administration in each treatment period.

**Section 6.1 of the CTP:** *Exact times of measurements outside the permitted time windows will be documented. The acceptable time windows for screening and the end of trial examination are provided in the CTP Flow Chart.*

*Study measurements and assessments scheduled to occur 'before' trial medication administration on Day 1 are to be performed and completed within a 3 h-period prior to the trial drug administration.*

*The acceptable deviation from the scheduled time for vital signs, and laboratory tests will be  $\pm 60$  min.*

*Starting from a planned time of 48 hours after drug administration (and beyond) a time window of  $+\text{-} 120$  minutes will be allowed for all procedures.*

The acceptable deviations from the scheduled time for PK/PD blood sampling will be:

$\pm 15$  min for planned times  $>0:00$  and  $\leq 4$  h after trial drug administration

$\pm 30$  min for planned times  $>4$  h and  $<48$  h

$\pm 120$  min for planned times  $\geq 48$  h

The pre-dose sample at planned time -3h is to be drawn within a 3 h-period prior to the trial drug administration.

Adherence to time windows will be checked via the consistency check listings at the RPM.

Unscheduled measurements of laboratory data and vital signs data will be assumed to be repeat measurements of the most recent scheduled measurement (e.g. for follow-up or confirmation of a particular value). Therefore, unscheduled measurements will be assigned to the planned time point of the previous scheduled measurement.

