			8:00	16:00	Snack (voluntary) 	x		x			
			10:00	18:00		x					
			11:00	19:00	Dinner						
			12:00	20:00		x		x			x
		2	24:00	08:00	Breakfast (voluntary)  , discharge from trial site	x		x	x	x	
			34:00	18:00	Ambulatory visit	x					x
			3	48:00	08:00	x					x
		4	72:00	08:00	Ambulatory visit	x					x
			5	96:00	08:00	x					x
FU	4	8 to 21			End of trial (EoTrial) examination 	x				x	x

1. Subject must be informed and written informed consent obtained prior to starting any screening procedures. Screening procedures include physical examination, check of vital signs, ECG, safety laboratory (including drug screening), demographics (including determination of body height and weight, smoking status and alcohol history), relevant medical history, concomitant therapy and review of inclusion/exclusion criteria. Pharmacogenetic samples will be collected if needed.
2. The time is approximate; the procedure is to be performed and completed within the 3 h prior to drug administration.
3. If several actions are indicated at the same time, the intake of meals will be the last action.
4. At the end of the trial the EoTrial examination includes physical examination, vital signs, ECG, safety laboratory, recording of AEs and concomitant therapies.
5. Only urine drug screening and alcohol breath test will be done at this time
6. AEs and concomitant therapies will be recorded throughout the trial, but will be specifically asked for at the times indicated in the Flow Chart above.
7. Only in period 2 (Treatment Test)

## FLOW CHART – PART 2

Period	Visit	Day	Planned time (relative to drug administration) [h:min]	Approximate clock time of actual day [h:min]	Event and comment	Safety laboratory	PK dabigatran	PK BI 135894 and metabolite 	Vital signs (BP, PR)	Questioning for AEs and concomitant therapy 
SCR	1	-21 to -1			Screening (SCR) 	x			x	
2/3	2/3	1	-3:00	05:00	Admission to trial site	x 	x 	x 	x 	x 
			-0:30	07:30	High fat, high calorie breakfast					
			0:00	08:00	Drug administration					
			1:00	09:00			x			
			1:30	09:30			x			
			2:00	10:00	240 mL fluid intake		x			
			2:30	10:30			x			
			3:00	11:00			x	x		
			3:30	11:30			x			
			4:00	12:00	240 mL fluid intake		x			
			5:00	13:00			x	x		
			6:00	14:00	240 mL fluid intake, lunch 		x		x	x
			7:00	15:00				x		
			8:00	16:00	Snack (voluntary) 		x			
			10:00	18:00			x			

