### Drug-induced liver injury (DILI)

Although rare, a potential for drug-induced liver injury (DILI) is under constant surveillance by sponsors and regulators. Therefore, this trial requires timely detection, evaluation, and follow-up of laboratory alterations in selected liver laboratory parameters to ensure subjects' safety. See also Section [5.2.6.1.4](#), adverse events of special interest.

Proprietary confidential information © 2019 Boehringer Ingelheim International GmbH or one or more of its affiliated companies

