Urinalysis  (Stix)	Urine Nitrite (qual) Urine Protein (qual) Urine Glucose (qual) Urine Ketone (qual) Urobilinogen (qual) Urine Bilirubin (qual) Urine RBC/Erythrocytes (qual) Urine WBC/Leucocytes (qual) Urine pH	X X X X X X X X	- - - - - - - -
Urine sediment 	Only positive findings will be reported (for instance, the presence of sediment bacteria, casts in sediment, squamous epithelial cells, erythrocytes, leukocytes)		

1 A to be done at screening examination, B at Follow-up examination.

2 Microscopic examination if erythrocytes, leukocytes, or protein are abnormal in urine

3 Estimated glomerular filtration rate according to CKD-EPI formula [\[R12-1392\]](#)

Proprietary confidential information © 2019 Boehringer Ingelheim International GmbH or one or more of its affiliated companies

The tests listed in Table 5.2.3: 2 are exclusionary laboratory tests that may be repeated as required. The results will not be entered in the CRF/database and will not be reported in the CTR. Except drug screening, it is planned to perform these tests during screening only. Drug screening will be performed at screening and prior to each treatment period.

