## 7.8.2 Laboratory data

The analyses of laboratory data will be descriptive in nature and will be based on BI standards [BI-KMED-BDS-HTG-0042] (10).

Laboratory data will be analysed qualitatively via comparison of laboratory data to their reference ranges. Values outside the reference range as well as values defined as possibly clinically significant will be flagged in the data listings.

Clinically relevant findings in laboratory data will be reported as baseline conditions (at screening) or as AEs (during the trial) if judged clinically relevant by the investigator, and will be analysed as such.

It is the investigator's responsibility to decide whether a lab value is clinically significantly abnormal or not (at the RPM/DBLM at the latest).

Descriptive statistics of laboratory data including change from baseline (=screening) will be calculated by planned time point based on the worst value of the subject at that planned time point (or assigned to that planned time point).

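### SAP 6.7 assigns an unscheduled post-dose laboratory value to screening, and the worst-value rule in SAP 7.8.2 then shows it in the screening row

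*SAP*

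**What the plan says.** SAP 6.7 states the assumption first, "Unscheduled measurements of laboratory data and vital signs data will be assumed to be repeat measurements of the most recent scheduled measurement", and then the rule: "Therefore, unscheduled measurements will be assigned to the planned time point of the previous scheduled measurement". Neither sentence excludes a value taken after an intervening dose. The same section gives a general baseline: "The baseline value is defined as the last measurement before trial medication administration in each treatment period".

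SAP 7.8.2 summarises laboratory data by planned time point, "based on the worst value of the subject at that planned time point (or assigned to that planned time point"), and describes the statistics as "including change from baseline (=screening").

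The routine laboratory schedule is short. Footnote 1 to Protocol Table 5.2.3: 1 reads "A to be done at screening examination, B at Follow-up examination". The laboratory entry before dosing on Day 1 is not a routine panel; footnote 5 of both Flow Charts says "Only urine drug screening and alcohol breath test will be done at this time".

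Protocol 5.2.6.1.4 foresees an unscheduled blood test when a subject has clinical symptoms of hepatic injury and no liver results are available.

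**The concern.** A repeat taken to confirm an abnormal screening result belongs with screening. A test taken after dosing because the subject has symptoms does not, yet SAP 6.7 handles the two alike. With no routine panel between screening and follow-up, this covers the whole dosed interval. The value most likely to be misplaced is one prompted by a safety question.

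At stake is the meaning of one row of a descriptive table. The screening row should show subjects before any drug. Under the stated rules it can contain a value measured on treatment, which makes the pre-drug population look less normal than it was. If that value also served as baseline, a post-dose rise would appear as a fall by the end of trial.

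**Working it through.** **Where the value goes**

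1. Scheduled routine laboratory time points: screening and follow-up (Protocol Table 5.2.3: 1).
2. The Day 1 entry at -3:00 h is a urine drug screen and a breath test. Protocol 5.2.3 says drug-screen results are not entered in the database, so they cannot act as a time point for ALT or bilirubin.
3. For a routine value taken after either dose and before the end-of-trial examination, the previous scheduled measurement is therefore screening.
4. Protocol 7.3.4 does not correct this, because it also assigns measurements by planned time.
5. SAP 7.8.2 takes the worst value assigned to the time point. If the post-dose value is worse, it replaces the true screening value.

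**Length of the exposed interval.** Protocol 6.2.2 requires at least 7 days between doses, and the Flow Charts place the end-of-trial examination on Day 8 to 21. If that day counts from the Period 2 dose as Day 1 (an assumption), the shortest interval from first dose to end-of-trial panel is 7 + (8 - 1) = 14 days. With a 7-day wash-out and Day 21 it is 7 + (21 - 1) = 27 days. All of it maps to screening. The mapping itself does not depend on the assumption.

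**Size of the effect on the screening row.** The plan gives no figure to reproduce, and all ALT values here are assumed. Take n = 14 (Protocol 7.7), ALT 0.5x ULN at screening in everyone, and one subject with one unscheduled post-dose value U.

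- Mean = (13 × 0.5 + U) / 14
- SD = (U - 0.5) / √14

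| U (x ULN) | Mean | SD | Median | Maximum |
|---|---|---|---|---|
| none | 0.50 | 0 | 0.5 | 0.5 |
| 1 | 7.5/14 = 0.54 | 0.13 | 0.5 | 1 |
| 2 | 8.5/14 = 0.61 | 0.40 | 0.5 | 2 |
| 3 | 9.5/14 = 0.68 | 0.67 | 0.5 | 3 |

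At U = 3 the mean is (5.5 + 3)/12 = 0.71 with 12 subjects and (9.5 + 3)/20 = 0.63 with 20.

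**Change from baseline, only if the worst assigned value is the baseline.** Assume an end-of-trial ALT of 0.6x ULN in everyone. With the true screening value the mean change is +0.10. With U = 3 as that one subject's baseline it is (13 × 0.1 + (0.6 - 3))/14 = -1.1/14 = -0.08, and the subject's own change goes from +0.1 to -2.4. The SAP does not say which of the two is meant.

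**Vital signs.** SAP 7.8.3 uses the last value at, or assigned to, the planned time point. In Part 2 vital signs are scheduled before dosing and next at 6:00 h, so an unscheduled reading in between is assigned to the pre-dose row and replaces the pre-dose reading there.

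**The case against.** The strongest reply is that the affected case is rare and the consequence small. Most unscheduled tests confirm an abnormal screening value before dosing or follow an abnormal end-of-trial value, and SAP 6.7 places both correctly. The one unscheduled test the protocol describes needs clinical symptoms of hepatic injury. If a subject discontinues, Protocol 3.3.4 calls for an end-of-trial examination where possible, and later repeats then map to that examination. The sponsor's laboratory standard (BI-KMED-BDS-HTG-0042) or the technical analysis data set plan may hold the missing exception. All of this stands and limits the size of the point. None of it changes what SAP 6.7 says, which is a stated rule without an exception.

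A reader might infer more than the documents support:

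- **Two competing laboratory baselines.** The per-period baseline in SAP 6.7 and the screening baseline in 7.8.2 differ for a value taken between doses. But 7.8.2 is the specific laboratory rule and reasonably governs, and the SAP specifies no laboratory table against a Period 2 baseline.
- **A very high between-dose value as Period 2 baseline.** An ALT of 10x ULN is a hepatic injury alert that calls for DILI-checklist follow-up (Protocol 5.2.6.1.4), and Protocol 3.3.4.1, item 5, then provides for discontinuation. Under those rules, once the value is known, there is no second dose and no Period 2 baseline.
- **The DILI paragraph in Protocol 1.4 as evidence of unscheduled tests.** It says "this trial requires timely detection, evaluation, and follow-up of laboratory alterations in selected liver laboratory parameters" but mentions no unscheduled test. The support comes from 5.2.6.1.4.
- **A vital-signs gap confined to Part 2.** Part 1 also has a pre-dose reading. The columns of its Flow Chart could not be read reliably enough to exclude the same gap there.

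**Conclusion.** The point holds for the screening row of the laboratory tables. Read as written, SAP 6.7 and 7.8.2 together let a worse post-dose value stand as the subject's screening value. An effect on change from baseline is possible but not established. Pre-dose vital-sign rows have the same gap for an unscheduled reading after dosing and before the next scheduled one.

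Severity is minor. A reader might infer that a safety signal could be lost, but the SAP does not support that: individual values are listed (Section 7), out-of-range values are flagged and clinically relevant findings are analysed as AEs (7.8.2), and AESIs have their own table (7.8.1). The PK endpoints are untouched. The numerical illustration rests wholly on assumed ALT values, and the documents do not say how often unscheduled tests occur. The sponsor's laboratory standard and the technical SAP were not available and could already contain an exception.

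**What to change.** In SAP 6.7, state that an unscheduled value taken after dosing is not assigned to screening or to that period's pre-dose time point, and is shown as an unscheduled on-treatment value under the actual treatment phase.

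In SAP 7.8.2, state that the laboratory baseline is the last value actually taken before the first dose, and that this overrides the per-period baseline in 6.7 for laboratory data.

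The cost is two or three sentences and a little extra programming for a row that will often be empty. No new data are needed. If the sponsor's laboratory standard already contains the exception, a cross-reference in 6.7 would cover the assignment rule.

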## 7. PLANNED ANALYSIS

If not stated otherwise, the trial parts will be evaluated separately.

Safety analysis (refer to [Section 7.8](#)) will be performed by \_\_\_\_\_ and will be presented in Sections 15.1 to 15.4 of the CTR and in Appendix 16.2 and 16.1.13.1.

Inferential statistical analyses of PK endpoints (refer to [Section 7.4](#) and [Section 7.5.2](#)) will also be performed by \_\_\_\_\_ and will be presented in Section 15.5 of the CTR and in Appendix 16.1.13.3.

Descriptive data analysis of PK/PD endpoints and concentrations will be performed by the \_\_\_\_\_ at \_\_\_\_\_ and will be presented in Section 15.6 and Section 15.7 of the CTR.

The format of the listings and tables will follow the BI standards (see BI-KMED-BDS-HTG-0045 ([6](#))) with the exception of those generated for PK-calculations ([7](#)).

The individual values of all subjects will be listed, sorted by sequence group, subject number, visit and actual treatment (if appropriate).

The listings will be included in Appendix 16.2 of the CTR.

For end-of-text tables, the set of summary statistics for non-PK parameters is:

N	number non-missing observations
Mean	arithmetic mean
SD	standard deviation
Min	minimum
Median	median
Max	maximum

For analyte concentrations, the following descriptive statistics will additionally be calculated:

CV	arithmetic coefficient of variation
gMean	geometric mean
gCV	geometric coefficient of variation

For PK/PD parameters, the following descriptive statistics will additionally be calculated:

CV	arithmetic coefficient of variation
gMean	geometric mean
gCV	geometric coefficient of variation
P10	10th percentile
Q1	1st quartile
Q3	3rd quartile
P90	90th percentile

The data format for descriptive statistics of concentrations will be identical to the data format of the respective concentrations. The descriptive statistics of PK parameters will be calculated using the individual values with the number of decimal places as provided by the evaluation program. Then the individual values as well as the descriptive statistics will be reported with three significant digits in the CTR.

Tabulations of frequencies for categorical data will include all possible categories and will display the number of observations in a category, as well as the percentage (%). Percentages will be rounded to one decimal place and will be based on all subjects in the respective subject set whether they have non-missing values or not. The category 'missing' will be displayed only if there are actually missing values.

Units of variables should be given in the titles or column/row descriptors in square brackets (e.g. [mg]).

#### Exclusion of PK parameters

The ADS ADPP (PK parameters) contains column variables indicating inclusion/exclusion (APEXC) of a PK parameter and an analysis flag comment (APEXCO). All analyses based on the PKS will include parameters if they are not flagged for exclusion, that is APEXC is equal to "Included".

#### Exclusion of PK concentrations

The ADS ADPC (PK concentrations per time-point or per time-interval) contains column variables ACEXC and ACEXCO indicating inclusion/exclusion (ACEXC) of a concentration and an analysis flag comment (ACEXCO). Exclusion of a concentration depends on the analysis flag comment ACEXCO. For example, if ACEXCO is set to 'ALL CALC', the value will be excluded for all types of analyses based on concentrations. If ACEXCO is set to 'DESC STATS' the value will be excluded from descriptive evaluations per planned time point/time interval. If ACEXCO contains the addition 'TIME VIOLATION' or 'TIME DEVIATION' the value can be used for further analyses based on actual times. If ACEXCO is set to 'HALF LIFE', the value will be excluded from half-life calculation (and, as a consequence, any calculation that relies on  $\lambda_z$ ) only; the value is included for all other analyses.

Further details are given in 001-MCS-36-472\_RD-01 "Noncompartmental Pharmacokinetic / Pharmacodynamic Analyses of Clinical Studies" ([5](#)) and 001-MCS-36-472\_RD-03 "Description of Analytical Transfer Files and PK/PD Data Files" ([11](#)).

## 7.1 DEMOGRAPHIC AND OTHER BASELINE CHARACTERISTICS

Only descriptive statistics are planned for this section of the report, based on the TS.

The data will be summarised in total, separately for trial part 1 and part 2.

## **7.2 CONCOMITANT DISEASES AND MEDICATION**

Frequency tables are planned for this section of the report, based on the TS.

Concomitant diseases will be coded using the coding system of the Medical Dictionary for Drug Regulatory Activities (MedDRA). Medications will be coded using the World Health Organization Drug Dictionary (WHO-DD). The coding version number will be displayed as a footnote in the respective output.

The diagnoses and medications will be listed. Subjects without any concomitant diagnoses or concomitant therapies should be marked with a “No” in the respective column.

The relevance of the concomitant therapies to the evaluation of PK will be decided no later than at the RPM.

## **7.3 TREATMENT COMPLIANCE**

**Section 4.3 of the CTP:** *Compliance will be assured by administration of all trial medication in the study centre under supervision of the investigating physician or a designee. The measured plasma concentrations of trial medication will provide additional confirmation of compliance.*

It is not intended to list the compliance separately. Any deviations from complete intake will be addressed in the RPM (cf. TSAP [Section 6.2](#)) and described in the CTR.

## **7.4 PRIMARY ENDPOINTS**

Relative bioavailability of rosuvastatin (part 1) and dabigatran (part 2) is to be determined on the basis of the primary endpoints  $AUC_{0-\infty}$ ,  $C_{max}$  (see [Section 5.1](#)).

### **7.4.1 Primary analysis of the primary endpoints**

**Section 7.3.1 of the CTP:** *The statistical model used for the analysis of the primary endpoints will be an analysis of variance (ANOVA) model on the logarithmic scale. That is, the PK endpoints will be log-transformed (natural logarithm) prior to fitting the ANOVA model. This model will include effects accounting for the following sources of variation: subjects and treatment. The effect ‘subjects’ will be considered as random, whereas ‘treatment’ will be considered as fixed. The model is described by the following equation:*

$$y_{km} = \mu + s_m + \tau_k + e_{km}, \text{ where}$$

- $y_{km}$  = logarithm of response measured on subject  $m$  receiving treatment  $k$ ,
- $\mu$  = the overall mean,

- $s_m$  = the effect associated with the  $m^{th}$  subject,  $m = 1, 2, \dots, n$
- $\tau_k$  = the  $k^{th}$  treatment effect,  $k = 1, 2,$
- $e_{km}$  = the random error associated with the  $m^{th}$  subject who received treatment  $k.$

where  $s_m \sim N(0, \sigma_w^2)$  i. i. d. ,  $e_{km} \sim N(0, \sigma_w^2)$  i.i.d. and  $s_m, e_{km}$  are independent random variables.

Point estimates for the ratios of the geometric means (test/reference) for the primary endpoints (see Section 2.1) and their two-sided 90% confidence intervals (CIs) will be provided.

For each endpoint, the difference between the expected means for log(T)-log(R) will be estimated by the difference in the corresponding adjusted means (Least Squares Means). Additionally their two-sided 90% confidence intervals will be calculated based on the residual error from the ANOVA and quantiles from the t-distribution. These quantities will then be back-transformed to the original scale to provide the point estimate and 90% CIs for each endpoint.

The implementation for this analysis will be accomplished by using the CSD macros. The following SAS code can be used:

```
PROC MIXED DATA=indata;
  CLASS subject treatment;
  MODEL logkp = treatment / HTYPE = 2 SOLUTION CL alpha=0.1;
  RANDOM subject;
  LSMEANS treatment /CL alpha=(1-&CONFLEV/100) pdiff=control("Ref_trt");
RUN;
```

## **7.5        SECONDARY ENDPOINTS**

### **7.5.1      Key secondary endpoints**

This section is not applicable as no key secondary endpoint has been specified in the protocol.

### **7.5.2      Secondary endpoints**

The secondary PK parameter  $AUC_{0-tz}$  for rosuvastatin (part 1) and dabigatran (part 2) will be assessed using the same methods as described for the primary endpoints.

## **7.6.2      Safety endpoints**

Refer to TSAP [Section 7.8](#) for a description of the analysis of safety and tolerability of BI 1358894.

